AF is a symptom of underlying cardiovascular risk factors and a marker of increased mortality and morbidity. We need to shift our focus to the treatment of these underlying risk factors in patients with AF. Diet, exercise, and risk factor management can be used to modify these risk factors both in the short term, and potentially with sustained effect. This study employs a randomized design to test a six-month supervised intensive exercise, diet, and risk factor management program, followed by a six-month home-based exercise and diet program. Based on previous studies, we hypothesize that this should lead to an improvement in cardiovascular risk factors, a reduction in AF burden, and possible improvements in left atrial remodeling.

3. Hypotheses:

- i) Patients with paroxysmal non-valvular AF that complete a supervised six-month program of exercise, diet, and life style modification will exhibit reduced recurrent AF and reduced cardiovascular risk factors when compared to a similar group of patients who receive usual care.
- ii) The intervention group will show improvements in physical fitness, cardiovascular risk factors, and AF symptoms and severity at both the six-month and one-year follow-up assessments compared to the usual care group.
- iii) A reduction in medication costs and emergency room visits will help offset the cost of the intervention.

4. Objectives: The objectives of this study are to demonstrate changes in symptoms and severity of AF following an exercise, diet, and risk factor modification intervention in patients with AF. Demonstrating that a comprehensive cardiac rehabilitation program is feasible and cost-effective will help us design a future larger-scale, multi-centre study.

i) Primary outcomes include:

- a. Burden of AF, including both frequency and symptoms.
 - i. The frequency of AF will be measured with 48-hour Holter monitor recording, looking at percent of time in AF at baseline, six months and one year follow up.

- ii. Symptoms of AF will be assessed using the Canadian Cardiovascular Society Severity in Atrial Fibrillation Scale (CCS-SAF) (31), and the Atrial Fibrillation Symptom Severity Scale (AFSS) (32); both are validated tools to assess burden of AF symptoms.
- iii. The 36-item Short Form Survey Instrument (33) and the EQ-5D-3L (34) will be used to measure quality of life.

ii) Secondary outcomes include:

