- a. Left atrial remodeling will be measured by LA volume index, diastolic function grade, and estimate of LA pressure via echocardiography at baseline and one year follow-up.
- b. Cardiovascular risk factors will be compared at baseline, six months and one year. These include: Systolic Blood Pressure, Hemoglobin A1C (marker of average blood sugar over 3 months), body mass index, waist circumference, and low density lipoprotein (LDL cholesterol), apnea hypopnea index (AHI), and fitness classification (metabolic equivalents (METS) achieved on exercise stress test).
- c. Using pharmanet data, total cost of all medications and specific cost for antiarrhythmic agents, antihypertensive agents, diabetes and cholesterol lowering medications will be recorded and compared at baseline and one year. Hospital Emergency visits will also be compared.

5. Methodology

5.1 Proposed Study Design: This is a parallel-group randomized controlled trial. Consecutive patients meeting eligibility criteria that are seen for routine cardiology follow-up, or those referred by family physicians, will be invited to participate in this study. Patients who accept the possibility of a year-long diet counseling and exercise program will be randomized and stratified to ‘control arm’ *versus* ‘intervention arm.’ Forty patients will be randomized to control arm and 40 patients randomized to the intervention arm. Intervention will include Phase 1, a six month program including three months of diet counseling combined with home exercise, followed by three months (starting at week 13) of an in-hospital, Cardiac rehabilitation exercise program. Phase 1 also includes risk factor management by an internist who specializes in cardiovascular risk factors. Phase 2 of the intervention will include six months of home-based maintenance exercise and diet (starting at week 25). Assuming approximately 40% of eligible patients agree to participate (based on our experience that there is a high willingness to participate in both research studies and the cardiac rehabilitation program), and given that we were able to recruit 200 research participants in one year for a previous study (35), we estimate that it is feasible to recruit a total of 80 participants over a three to six month period.

5.2 Participants: Patients will provide written, informed consent. All study procedures will be reviewed and approved by the UBC Clinical Ethics board and the VCH operational approval process.

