5.4 Data Collection

All measurements (save demographics and medical history) will be collected at baseline, six months, and one year in both groups.

1. Patient demographics: age, sex, ethnicity, education, income, and living situation.
2. Medical history: medications and cost; hospital emergency visit and admission < 1yr, known coronary artery disease defined by prior myocardial infarction or presence of 50% stenosis on CT or invasive angiogram; admission for heart failure, prior stroke; average daily glasses of alcohol, smoking status (including frequency and amount); the Canadian Cardiovascular Society Severity in Atrial Fibrillation (CCS-SAF) Scale, (31) the Atrial Fibrillation Symptom Severity Scale (AFSS) (32), the 36-item Short Form Survey Instrument (33) and the EQ-5D-3L (34).
3. Anthropometrics: Body mass index (BMI), waist circumference, neck circumference, modified mallampati score (41) and blood pressure.
4. Blood work: Hemoglobin AIC, total cholesterol, creatinine, low-density lipoprotein, high-density lipoprotein, triglycerides, ALT, c-reactive protein, electrolytes, and brain natriuretic peptide.
5. Level 3 home sleep study: Apnea-hypopnea index, minimum saturation, and time spent with saturation < 90%, Epworth Sleepiness Scale (42).
6. Godin's leisure time physical activity measure will be used measure baseline physical activity levels (43).
7. Exercise Stress Test at maximal effort: Maximum METs achieved, peak heart rate, and rating of perceived exertion.
8. 48-hour Holter monitor: 48-hour heart rhythm monitor to determine frequency and duration of AF measured as the percent of time in AF.
9. Echocardiography at base line and one year: measurements: LA volume, LA pressure, diastolic function, grade, calculated biplane LVEF, and left ventricular hypertrophy.

All data sheets are attached in section 9 of the application. There is a data sheet for each: sleep study, echo, blood work, stress test, physical exam, and Holter monitor.

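### Five instruments are listed as primary, but no primary variable, visit, success rule or multiplicity adjustment is named, so the error rate of the primary claim is not controlled

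*Combined protocol and SAP*

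**What the plan says.** Section 4 (Objectives, primary outcomes) gives one construct, "Burden of AF, including both frequency and symptoms", and three items beneath it:

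- Holter monitoring, "looking at percent of time in AF at baseline, six months and one year follow up";
- two AF symptom scales, CCS-SAF and AFSS;
- two general health instruments: "The 36-item Short Form Survey Instrument (33) and the EQ-5D-3L (34) will be used to measure quality of life".

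No instrument is singled out, and no score is named for any questionnaire. The opening sentence of the section puts the aim in terms of symptoms: "The objectives of this study are to demonstrate changes in symptoms and severity of AF".

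On timing, section 3 hypothesis (i) says that patients who "complete a supervised six-month program of exercise, diet, and life style modification will exhibit reduced recurrent AF". Hypothesis (ii) expects improvement, including in AF symptoms and severity, "at both the six-month and one-year follow-up assessments compared to the usual care group". The dissemination plans foresee an abstract on mid-point results and a final report after one-year follow-up.

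Section 5.4 (Data Analysis) specifies independent t-tests on differences from baseline, with significance at p<.05. It does not say which outcome or visit decides the primary claim, whether one or all results must be significant, or how multiplicity is handled.

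**The concern.** With five instruments and two post-baseline visits, ten between-group tests could each be presented as the primary result. Nothing in the text prevents the instrument or visit from being chosen once results are known. A reader of a positive report could not tell whether it was the one planned test, the best of ten, or a joint requirement that was met. These carry very different evidential weight.

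The trial is meant to inform a larger study, but it also states efficacy hypotheses and is sized to detect an effect, so its primary claim needs a defined error rate.

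**Working it through.** **Inputs from the documents.** Five primary instruments; two post-baseline visits; p<.05 per test; 40 per arm; an allowance of more than 10% dropout; effect sizes of 0.64 (fitness) and 1.0 (pre-post time in AF). The sample-size text is two-tailed, so I take 2.5% per test in favour of the intervention.

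**Assumptions.** The documents give no correlations. I take 0.3-0.7 between instruments and 0.3-0.7 between visits, with one score per questionnaire. For different instruments at different visits, the correlation is the product of the two.

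**The plan's own figure.** The only stated calculation is 22 per group for 80% power at d = 0.64. An exact two-sided paired t-test gives n = 21.2, rounded up to 22, so the figure reproduces as a within-group comparison. It does not define a primary outcome: 0.64 is a fitness effect, and fitness is a secondary outcome.

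**1. Any one significant result counts.** If the tests were independent, the rate would be 1 - 0.975^k: 11.9% for k = 5 and 22.4% for k = 10. With a common correlation r at one visit, it is

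1 - ∫ Φ((1.96 - √r·u)/√(1 - r))^5 φ(u) du.

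Two visits were done by multivariate-normal simulation.

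| Favouring the intervention | Instrument r = 0.3 | 0.5 | 0.7 |
|---|---|---|---|
| Five tests, one visit | 10.5% | 9.2% | 7.4% |
| Ten tests, visit r = 0.3 | 19.0% | 16.5% | 13.7% |
| Ten tests, visit r = 0.5 | 18.2% | 15.8% | 12.9% |
| Ten tests, visit r = 0.7 | 16.7% | 14.6% | 11.8% |

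At instrument correlation 0.9 the rate is still 5.1% at one visit, and 8-9% over two visits with visit correlation 0.5-0.7. Two-sided (nominal 5%), the one-visit range is 15-21% and the two-visit range 23-37%. More than one score per questionnaire would raise these figures.

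**2. Joint readings of the wording, same assumptions, favouring the intervention.**

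- Any one instrument significant at both visits: about 1-4%.
- Holter and at least one of the two symptom scales, at one visit: 0.4%, 0.8% and 1.2% at instrument correlation 0.3, 0.5 and 0.7.
- The same, with a free choice of visit: about 0.8-2.4%.

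**3. Power cost of the remedies.** Two-sample t-test with 36 per arm (40 less 10%):

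| Effect | alpha 0.05 | 0.0167 (Holm first step, three outcomes) | 0.01 (five outcomes) |
|---|---|---|---|
| d = 0.64 | 76% | 60% | 53% |
| d = 1.0 | 99% | 96% | 94% |

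For two co-primaries, each with d = 0.64, joint power lies between 0.764 × 0.764 = 58% (uncorrelated) and 76% (perfectly correlated). Neither effect size is established as a between-group effect on a primary instrument.

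**The case against.** The strongest reply is that the inflated rates need a rule that the plan never states. The rule-like wording it does contain is joint: both frequency and symptoms in section 4, and both visits in hypothesis (ii). On those readings the rate is below or near nominal. This stands, and it is why the inflation is only one scenario. It does not close the gap, because neither phrase is carried into section 5.4 as a decision rule, and hypothesis (ii) does not choose among instruments.

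Other points have some weight. Time in AF is listed first and is the only primary instrument in the sample-size text, which hints at priority without declaring it. The analyst is blinded to group, and results are to be published whatever their direction. Neither safeguard fixes which result is the primary one. The trial is partly preparatory, which lowers the stakes but does not remove the efficacy hypotheses.

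Three stronger readings are tempting, and the documents do not support them.

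- *The visits contradict each other.* Hypothesis (i) describes patients who complete six months of treatment; it does not fix an assessment visit. A final report at one year is compatible with hypothesis (ii). What can be said is that no primary visit is designated.
- *The mid-point abstract is an early primary test.* The text does not say that it will contain a between-group comparison.
- *Four of the five primary instruments have no follow-up.* Section 5.4 (Data Collection) says "All measurements (save demographics and medical history) will be collected at baseline, six months, and one year in both groups" and files the questionnaires under medical history. Read literally, that exempts them. But hypothesis (ii) needs symptoms at follow-up, and emergency visits sit in the same item although section 4 says "Hospital Emergency visits will also be compared". It looks like a filing slip and is a separate, minor matter.

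**Conclusion.** The concern holds as an undefined primary claim. As written, the plan leaves the false-positive rate for that claim anywhere from about 0.4% to about 19% in favour of the intervention, against a nominal 2.5%, depending on a rule the sponsor has not stated. A reader might infer that the plan has a 7-19% error rate. That would be true only if any one significant result were allowed to count, and only under the assumed correlations. The absence of a rule comes from the text itself and needs no assumption. It should be settled before any comparison of the arms, because a choice made afterwards cannot be shown to be independent of the results.

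**What to change.** Before any between-group comparison, including any for the mid-point abstract, state one of these in section 4 and in section 5.4 (Data Analysis). The choice is the sponsor's.

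- **(a) One primary.** *The primary outcome is the between-group difference in change from baseline in [variable] at [visit], tested at two-sided 0.05; all other outcomes are secondary and reported as estimates with 95% confidence intervals.* Percent time in AF is one candidate, as the only primary instrument in the sample-size text. Cost: no power is lost to multiplicity, but the other outcomes and the other visit can no longer support a primary claim.
- **(b) Co-primaries.** Percent time in AF and one named symptom score must both be significant at the named visit or visits. This is closest to the protocol's wording and needs no split of alpha. Cost: lower power, 58-76% for two outcomes at one visit under the assumptions above, and less if both visits must succeed.
- **(c) Several primaries at one named visit, with Holm.** Cost: at d = 0.64 and 36 per arm, first-step power falls from 76% to 60% with three outcomes or 53% with five.

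If a questionnaire is primary, name the score. Label the mid-point abstract as primary or secondary according to the visit chosen. As a separate clarification, list the questionnaire visits outside the medical history item in section 5.4 (Data Collection). All of this is wording; no procedure or visit changes.

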Inclusion Criteria: Patients with paroxysmal, non-permanent, non-valvular AF who have a $BMI \geq 27 \text{ kg/m}^2$, or central obesity using abdominal circumference with ethnicity-specific values recommended by Canadian diabetes association (36); plus one of hypertension, diabetes, moderate or severe sleep apnea, or consumption equal to or greater than three glasses of alcohol per day. Participants must be over 18 years of age and under 75 years.

Exclusion Criteria: Patients with permanent AF, estimated survival less than 2 years, left ventricular ejection fraction $< 40\%$, and/or prior cardiac valve surgery. Other exclusions include: inability to walk on a treadmill, defibrillator, entry exercise test positive for ischemia (37), and/or absolute and relative contraindications to exercise testing (37).

5.3 Study Procedure: All participants will undergo baseline, maximal effort exercise testing described in data collection section 5.4. Peak heart rate (HR_{peak}), total METS, and Borg rating of perceived exertion scale will be recorded (37). Maximal exercise tests will be repeated at six months and one year in all participants. All participants in the intervention and control arms will be screened for obstructive sleep apnea with a home sleep apnea test (level three study). [name] (Respirologist at Richmond hospital) will assess any patients with at least moderate sleep apnea, an apnea hypopnea index over 20. [name] has expertise in sleep apnea and is a co-investigator of this study. CPAP will be recommended and for one year for patients with apnea hypopnea index of > 30 , or > 20 with excessive day time sleepiness. CPAP machines will be loaned by the sleep clinic to patients who do not have insurance coverage for one year. LA volume index, pressure and grade of diastolic dysfunction will be measured by echocardiography at baseline and one year. The same technician will perform all echocardiograms using the same echocardiogram machine, and one cardiologist blinded to participant’s study arm will review the results.

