5.4 Data Analysis (and sample size)

This is a parallel, randomized control study. The researcher analyzing results will be blinded to the patient's group. A statistician will be hired to analyze data and a statistician from C2E2 (UBC) has reviewed the study design. Normally distributed data will be analyzed using repeated measures analysis of variance (ANOVA) to calculate changes over time (baseline, six-months, one-year) within each group. Between groups analyses on differences from baseline will be analyzed using independent *t*-tests. Statistical significance will be set *a priori* as *p*<.05. Continuous variables will be described by group using mean (SD) (or median (P25, P75) if the data are skewed); and categorical variables will be described by frequency (percent).

To calculate effect size for the intervention group, we considered the moderate effect sizes reported in exercise studies measuring cardiorespiratory changes (e.g., Huang et al. (2016) (40) reported a moderately high effect size of 0.64 for aerobic changes following an exercise program in older adults). Using G-power software (*alpha* = .05), the

sample size required to achieve 80% power to detect an effect is 22 per group (two-tailed, or repeated measures design) (44). Based on the data from Malmo and colleagues (26) reporting a large effect size (1.0) for the difference in time spent in AF pre- and post-exercise, a sample size of less than 10 participants would achieve a power of 80%. The AF studies to-date report low attrition rates. For example, Pathak et al. (19) reported 10% attrition in the risk factor intervention group, and Malmo et al.(26) reported a 0% attrition in the three-month interval-training program. Given that the Richmond Cardiac Rehabilitation program similarly reports low drop-out rates (of approximately 2%), we have allowed for greater than 10% attrition. Including 40 participants in the intervention arm, and 40 participants in the control arm will allow for more than 10% drop out while still maintaining adequate power to detect an effect.

6. Summary and Impacts on Practice

Richmond has experience in recruiting patients with AF, cardiac rehabilitation, and bariatric diet therapy program. Our Richmond team of specialists, combined with strong partnerships with our colleagues at VGH that have experience with research trials will help guide us in implementing a successful research project.

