This study uses a reproducible intensive supervised cardiac rehabilitation program that includes exercise, diet, and risk factor modification for patients with paroxysmal, non-valvular AF. We expect that a six-month intervention will show significant improvement in fitness and weight loss and improvements in AF symptoms and frequency, and cardiovascular risk factors when compared to a control group with paroxysmal AF and similar baseline characteristics who do not receive a supervised diet and exercise program. The supervised program is followed by a six-month home-based exercise and diet program, which gives us the opportunity to look further at adherence, and whether the benefits of the six-month intensive hospital-based program can be sustained at home. A follow-up study could retest the baseline results at two years and up to five years if effects are sustained. If both the phase 1 cardiac rehabilitation and diet six-month program and phase 2 home-based program are successful, then this study could be repeated with only a home-based or community-based intervention as a lower cost alternative.

The missing piece in studies of antiarrhythmic therapy and catheter ablation for patients with paroxysmal AF is the inclusion of risk factor modification. With attention to diet, exercise, and cardiovascular risk factor modification it should be possible to obtain high rates of maintenance of normal sinus rhythm. This exercise, diet and risk factor modification model can be added to usual care or catheter ablation aiming for optimal five-year reduction in AF. Alternatively patients could be randomized to diet and exercise, versus usual care post-catheter ablation. In future trials, a loop recorder could possibly be implanted to give more accurate information of AF recurrence rates.

Future studies with longer follow up can also focus on a more robust cost benefit analysis. Demonstrating that an exercise and diet intervention is cost-effective and efficacious in reducing the burden of AF can potentially be used to encourage government funding and physicians to prescribe exercise and diet to all patients with paroxysmal AF. Ultimately a large, multi-centre trial that combines exercise, diet, and risk factor modification in patients with paroxysmal AF compared to usual care can be designed to determine whether this intervention reduces mortality, cardiac events, and stroke.

Dissemination plans:

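### One 48-hour Holter per visit estimates AF burden imprecisely and cannot establish recurrence; a baseline-adjusted repeated-measures model would use the same recordings better than the planned change-score t-test

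*Combined protocol and SAP*

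**What the plan says.** Section 4 makes AF frequency one part of the primary burden outcome, beside symptom scales and quality of life: "The frequency of AF will be measured with 48-hour Holter monitor recording, looking at percent of time in AF". There are three recordings per participant, one before treatment and one at each of the two follow-up visits. The Data Collection section lists the same measure: "48-hour Holter monitor: 48-hour heart rhythm monitor to determine frequency and duration of AF measured as the percent of time in AF". It is the only rhythm measure in the plan.

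Section 3, hypothesis (i), says that patients completing the six-month programme "will exhibit reduced recurrent AF and reduced cardiovascular risk factors when compared to a similar group" under usual care. No recurrence endpoint is defined. Hypothesis (ii) asks for effects at six months and at one year, and Section 5.3.2 adds the question of whether six-month results last to one year.

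Eligibility in Section 5.2 begins "Patients with paroxysmal, non-permanent, non-valvular AF" and sets no minimum burden.

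The Data Analysis section plans repeated-measures ANOVA over the three visits within each group. For the arms it says: "Between groups analyses on differences from baseline will be analyzed using independent" t-tests. It names no primary time point and no baseline adjustment. Section 6 remarks that in future trials "a loop recorder could possibly be implanted to give more accurate information of AF recurrence rates".

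**The concern.** Two things do not fit.

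First, the hypothesis and the measurement are different quantities. Recurrence concerns whether episodes happened over a period. Percent time in AF over two days says nothing about the rest of that period.

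Second, paroxysmal AF comes and goes, so a two-day reading depends partly on whether an episode happened to fall inside the window. A change score subtracts one such reading from another. If repeat recordings in the same patient correlate weakly, the subtraction adds variance rather than removing it. The only objective rhythm component of the primary outcome would then be compared less precisely than the data allow, in a trial with 40 patients per arm that is meant to inform a larger one.

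**Working it through.** **The plan's own figures.** The Data Analysis section gives 22 per group for an effect size of 0.64 (aerobic fitness) and fewer than 10 participants for a pre-post effect size of 1.0 in time in AF; 80% power, alpha 0.05, two-tailed. A paired t-test at 0.64 gives n = 22 (power 0.817), so the first figure reproduces as a within-group calculation. At 1.0 a paired test needs 10 (n = 9 gives 0.748), close to the stated figure. The between-arm t-test needs 40 per arm at 0.64 and 17 per arm at 1.0. Neither stated figure rests on a between-arm effect or an SD for the Holter measure.

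**Coverage.** 26 weeks × 168 h = 4,368 h; 48 / 4,368 = 1.1%.

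**Share of sampling variation.** The documents give no inputs, so these are assumed: each patient alternates between AF and sinus rhythm with exponential durations; median burden 1% to 20%; between-patient SD of logit burden 1.0 or 1.5; mean episode 2 to 24 h; 40 scenarios. The noise share is the within-patient variance of a 48-hour reading divided by its total variance.

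| Median burden | Logit SD | Mean episode | Noise share | AF-free on one Holter | AF-free on both follow-ups |
|---|---|---|---|---|---|
| 1% | 1.0 | 24 h | 96% | 95% | 91% |
| 5% | 1.0 | 12 h | 80% | 71% | 55% |
| 5% | 1.5 | 12 h | 57% | 67% | 53% |
| 20% | 1.5 | 2 h | 13% | 10% | 5% |

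The share clearly exceeded 50% in 25 of 40 scenarios. Every simulated patient has paroxysmal AF, so an AF-free recording here never means absence of AF. Constant burden within a patient is also assumed; clustering of episodes would raise the share.

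**Variance of the arm comparison.** Assume equal variance (set to 1) at all visits and a common correlation r between visits. Per-patient variance:

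- Planned change score, one visit: 2(1 − r).
- One visit, baseline as covariate: 1 − r². Ratio to plan: (1 + r)/2.
- Mean of both follow-ups minus baseline: 1.5(1 − r). Ratio: 0.75 at any r.
- Mean of both follow-ups, baseline as covariate: (1 + r)/2 − r² = (1 − r)(1 + 2r)/2. Ratio: (1 + 2r)/4.

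| r | Adjusted, one visit: ratio (cut) | Adjusted, average: ratio (cut) |
|---|---|---|
| 0.1 | 0.55 (45%) | 0.30 (70%) |
| 0.5 | 0.75 (25%) | 0.50 (50%) |
| 0.9 | 0.95 (5%) | 0.70 (30%) |

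**What this means for power.** Take 36 per arm (40 less 10%) and an assumed standardised effect of 0.5 on the single-visit change score, equal at both visits. The planned test has power 0.55. One adjusted visit has 0.81, 0.68 or 0.57 at r = 0.1, 0.5 or 0.9, and the adjusted average 0.97, 0.84 or 0.71. The 0.5 is only an illustration. It is held fixed on the change-score scale, so compare methods at one r, not across r.

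**When averaging stops helping.** If the smaller visit effect is a fraction f of the larger, the average gains over the better visit only if (1 + f)/2 exceeds the square root of the variance ratio. Within the baseline-adjusted model that ratio is (1 + 2r)/(2(1 + r)), so f must exceed 48%, 63% or 72% at r = 0.1, 0.5 or 0.9. With unadjusted change scores the threshold is 2√0.75 − 1 = 73%.

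**The case against.** The best defence is that noise is not bias. If recordings are scheduled without regard to symptoms, each Holter is unbiased for burden near its visit, and the randomised comparison of means is valid. That stands.

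A reader might infer from 1% coverage that the reading is mostly noise and that a real reduction will probably be missed. The documents support neither. The noise share depends on burden, episode length and between-patient spread, none of which is given, and falls to 13% within the assumed range. No between-arm effect on the Holter is stated, so the chance of missing one cannot be computed.

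A reader might also take Section 6 to concede that a loop recorder is required, or expect AF-free participants to be classed as recurrence-free. Section 6 only raises a recorder as a possibility for future trials, and the plan defines no recurrence-free status.

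Finally, it is tempting to make the average of the two follow-up Holters the main estimate, since it needs no new data. That would merge the supervised and home phases, although the trial asks about six months and about persistence. If the smaller effect is half the larger, averaging change scores lowers power from 0.76 to 0.64 (effect size 0.64 at the better visit, 36 per arm). This part of the objection stands, and the average belongs in a supportive role.

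**Conclusion.** The point holds in a limited form. The mismatch between recurrence in hypothesis (i) and a two-day burden measure follows from the text alone. That a single reading may be dominated by sampling variation is plausible over much of the assumed range but not established. The comparison of mean burden is unbiased but imprecise.

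The planned change-score t-test is less precise than a baseline-adjusted comparison of the same recordings at every correlation below 1. The gain is large when repeatability is poor (45% of variance per visit at r = 0.1) and small when it is good (5% at r = 0.9). These figures rest on equal variances and a common visit correlation, neither of which the documents allow one to check.

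**What to change.** For the Holter outcome, replace the independent t-tests with one between-arm repeated-measures model of the six-month and one-year recordings, with baseline percent time in AF as covariate and arm-by-visit terms.

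- Report the arm difference at each visit. These answer the six-month and sustained-effect questions.
- Prespecify the average over both visits as supportive, not as a replacement.
- Since many recordings may show no AF, use inference that tolerates many zeros, such as robust standard errors or a permutation test.
- State how a participant with one missing Holter is handled.
- In hypothesis (i), claim lower percent time in AF on 48-hour Holter instead of reduced recurrence, and state that an AF-free recording is not evidence of no recurrence.

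The cost is a paragraph in the Data Analysis section and a wording change in Section 3. No recordings are added, and the visit-specific target, the difference in mean percent time in AF, is unchanged. The average is diluted where the effect differs between visits, which is why it stays supportive.
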